### 3. Assessment measures

Comprehensive assessment of psychiatric comorbidities (e.g., depression, anxiety) are critical for testing study hypotheses. A semi-structured psychiatric diagnostic interview and DSM-IV criteria will be used to make the diagnosis of any co-morbid psychiatric conditions.

- (1) The Research Diagnostic Questions for Adult Functional GI Disorders in order to satisfy the presence of FGID(s) based on established diagnostic criteria (Rome III).
- (2) The Gastrointestinal Symptom Questionnaire (GISQ) which contains the following questionnaires:

- a) GI symptom assessment (GISQ Part A):
  - 1. two 100-mm visual analog scales assessing recent bowel symptom burden and severity, and
  - 2. a quantification of bowel symptom frequency
- b) Somatization state and trait measures (GISQ Part B):
  - 1. the PHQ-15 somatization form, a validated self-report of recent somatic symptoms (somatization state measure), and
  - 2. a somatization diagnosis checklist (somatization trait measure).
- c) Mood disorder measures (GISQ Part C):
  - 1. the Beck Depression Inventory
  - 2. the Beck Anxiety Inventory
- d) Health-related quality of life measures (GISQ Part D & E):
  - 1. the Short-Form General Health Survey-36 (SF-36), an instrument applied previously in the assessment of health influence on global well-being in FGID and other somatic disorders.
  - 2. a visual analog scale assessment of global symptom response to therapy.
- e) FGID treatment measures (GISQ Part D):
  - 1. a visual analog scale assessments of GI symptom response to therapy.
  - 2. a self-report of subject compliance with medical therapy.
  - 3. a validated questionnaire measuring beliefs about medications.

(3) The Gastrointestinal Symptoms Questionnaire Supplement (GISQ-S) which contains the following questionnaires:

- a) State-Trait Anxiety Inventory for Adults (STAI) (Part A). The State-Trait Anxiety Inventory Form Y (STAI) is an instrument for measuring anxiety in adults. The STAI differentiates between the temporary condition of "state anxiety" and "trait anxiety." The qualities evaluated by the STAI-Anxiety scale are feelings of apprehension, tension, nervousness, and worry.
- b) Pain Catastrophizing Scale (PCS) (Part B) is widely used to assess cognitive and affective responses to pain and to evaluate pain management program outcomes.
- c) Somatic Symptoms Inventory (SSI) (Part C): The SSI is a self-report questionnaire composed of 26 bodily complaints drawn from the hypochondriasis scale of the Minnesota Multiphasic Personality Inventory and the Hopkins Symptom Checklist somatization scale.
- d) SOMS-7 (Part D) is a 7-item instrument for the evaluation of treatment effects in somatoform disorders. It covers all somatic symptoms mentioned as occurring in somatization disorder, according to DSM-IV and ICD-10.
- e) Gastrointestinal Symptom Rating Scale for IBS (GSRS-IBS) (Part E): The Gastrointestinal Symptom Rating Scale is a disease-specific instrument that includes 15 items combined into five-symptom clusters addressing different gastrointestinal symptoms. The five-symptom clusters depict reflux, abdominal pain, indigestion, diarrhea and constipation. The GSRS has a seven-graded Likert type scale where 1 represents absence of bothersome symptoms and 7 very bothersome symptoms. The GSRS is well documented to be reliable and valid and norm values for a general population are available.
- f) Life-Stress Questionnaire. (4) Additional questionnaire measures
  - a) SES Ladder (SES-L)
  - b) Brief Pain Inventory (BPI)
  - c) Hospital Anxiety and Depression Scales (HADS)
  - d) Coping Strategies Questionnaire-Catastrophizing scale (CSQ-C)
  - e) IPIP Neuroticism and Extroversion scales (IPIP-NEO)
  - f) Early Trauma Inventory-Self Report (ETISR)

g) Positive and Negative Affect Scales (PANAS-SF)

(5) Diet Assessment

a) Harvard School of Public Health Food Frequency Questionnaire (FFQ):

<https://regepi.bwh.harvard.edu/health/FFQ/files/2007%20BOOKLET%20FFQ.pdf>

### **C. Functional neuroimaging testing.**

1. Rectal balloon placement/distention. A rectal latex balloon with an external diameter of 5 cm and a length of 9 cm (Mui Scientific, Canada) will be placed with its distal end 4 cm from the anal verge. A 20 min rest period will elapse to allow the patient to become acclimated to the presence of the rectal balloon before initiation of the protocol. The rectal balloon catheter will be attached to a one end of silastic tubing, and the remaining end of the tubing attached to the rectal balloon will be connected to a barostat, a device designed to safely deliver controlled inflation of a rectal balloon at pre-determined pressures following a programmed protocol.

2. Dolorimetry methodology. A pre-MRI baseline session will be performed to determine a tolerance for pressure pain sensitivity thresholds. A discrete pressure stimulus of 40 seconds will be applied to the left thumbnail using a 1-cm^2 hard rubber probe attached to a hydraulic piston as described previously. Dolorimetry using standard thumb pressure has been shown to accurately and reproducibly reflect an individual's overall pressure-pain sensitivity. A pressure of 1.4 kg-cm^2 will be applied during the stimulus period, as this is the threshold previously established as "moderate" on a pain scale used in a fibromyalgia population.

3. Structural MRI scan. All scanning will be performed on a 3.0T Siemens Allegra MR scanner at the WU Center for Clinical Imaging Studies (CCIR). Acquisition of a scout scan with three orthogonal slices, followed by a coarse 3D sagittal T1-weighted MP-RAGE (magnetization prepared rapidly acquired gradient echo) will be used in slice registration. The coarse MP-RAGE will be used to automatically compute fMRI slice tilts and offsets that optimize whole brain. High-resolution structural images will be acquired using a 3D sagittal T1-weighted MP-RAGE acquisition optimized for contrast-to-noise and resolution. High-resolution multislice oblique axial spin density/T2-weighted fast spin echo (FSE) structural images will be acquired using slice tilts and positions computed by slice registration. The acquisition of T2-weighted data with slice pre-registration provides very similar slice positions in serial studies. The T2-weighted FSE data will be used in the fMRI atlas registration procedure.

4. Functional MRI (fMRI) scanning. Functional images will be collected in runs using asymmetric spin-echo echo-planar sequence (same as blood oxygen level-dependent, "BOLD", contrast (T2\*)). Each functional run will consist of sets of 39 contiguous 3.2 mm thick axial images acquired parallel to the anterior-posterior commissure plane, allowing complete brain coverage at high signal-to-noise ratio. MRI data will be reconstructed into images, then normalized across runs by scaling whole-brain intensity signal to a fixed value and, removing the linear slope on a voxel-by-voxel basis to counteract effects of drift. MR data will be aligned to correct for head motion using a six-parameter rigid body rotation and translation correction which mutually registers all frames in all runs for each subject. Between-subjects analyses will be conducted after transforming data to a common atlas space and then blurring images with an optimal Gaussian filter To transform MR data into standard atlas, T1-weighted MP-RAGE and T2-weighted FSE anatomic images will be obtained (see above). This overall strategy has been described previously. A sequence of linear (affine) transformations will be computed involving a combination of intra- and cross-modal registration procedures (e.g., T2- or T2\*-weighted EPI to FSE to MP-RAGE to an atlas-representative MP-RAGE target). The transforms are combined by matrix multiplication such that reslicing of data in conformity with the atlas then will involve only one interpolation. The cross-modality registration algorithm used for this procedure is related to methods described previously. The intra-modality registration algorithm is equivalent to minimization of difference image variance. This is identical to the method used for MR-based co-registration of PET data This method provides a straightforward means of conducting quantitative group comparisons while preserving the enhanced temporal resolution of fMRI. This analysis technique has been validated against single-subject analyses conducted with the N-back test.

**6. Rectal balloon distention/dolorimetry protocol.** All balloon distensions and dolorimeter activations will be performed with the participant in the supine position with eyes closed to minimize extraneous visual stimuli (potentially confounding fMRI data). Participants will be informed that a series of stimuli are about to be delivered

prior to a series of balloon distensions/thumb pressure deliveries, but will be given no insight into the degree of the impending distension or pressure. The balloon distension protocol will consist of a series of rectal balloon distensions and intermixed thumb pressure deliveries performed using a block design as reported previously. Each “fMRI block” will constitute a total of 6 (six) 40-second “Control periods” alternated with 6 (six) 40-second “Stimulus periods”. A continuous fMRI scan will be obtained for each of the fMRI blocks (Figure 11). Each 480-second fMRI block will be followed by a resting period of two (2) minutes between each functional scan for recovery of baseline MRI signal between scans. The individual fMRI blocks will randomly alternate two

(2) rectal balloon distensions of 25 mm Hg (sensation of stool or mild pressure), two (2) distensions of 50 mm Hg (sensation of moderate pressure or discomfort), and two (2) thumb pressure applications of 1.4 kg/m^2 (“Moderate pain”), with 40 second periods of rest interposed between these stimuli. Following fMRI rectal distention/dolorimeter protocol sequence, the participant will be removed from the MRI scanner using routine protocol.

Figure 12. Rectal balloon distention/dolorimetry protocol.

### Obtaining samples for genetic analysis.

We will obtain 5 ml of saliva using an established collection technique. All DNA samples will be collected by the principal investigator. Samples will be de-identified and delivered to the lab of [name] for single nucleotide polymorphism (SNP) genotyping. [name] is a molecular geneticist with more than 20 years’ experience studying the genetic basis of neuropsychiatric disease. His laboratory will employ a Pyrosequencer or Sequenom mass spectrometer for SNP genotyping. Using these technologies, to date [name] lab has genotyped several hundred SNPs in several thousand study subjects.

[figure not shown]
### Stool microbiome assay

Recent work has confirmed that, independent of bowel pattern, IBS patients possess different patterns of intestinal flora than control subjects with reduced microbial diversity and via detailed microbial examination using high-throughput pyrosequencing, the existence of IBS subgroups, with one IBS subgroup resembling controls, and the other with proportional differences in *Bacteroidetes* and *Firmicutes*. Further, the sensitivity to colonic distention was successfully transferred to germfree rats inoculated with the fecal microbiota from IBS patients.

**Sample collection (stool).** Patients will be provided a sterile stool sample collection container and sterile tongue depressors for sample acquisition. Stool samples will be collected as soon as possible, placed within sterile CryoVial tubes, snap-frozen in pre-cooled methyl-butane in dry ice, and stored at -80°C until use.

### Data Analysis and Sample Size Calculations

The proposed experimental include visceral and somatic stimuli which will be studied in a block design, and the obtained functional MRI activations will be analyzed using the general linear model, combined with appropriate corrections for multiple comparisons. These methods are implemented within a set of proprietary display and analysis tools developed by Washington University investigators within the Mallinckrodt Institute of Radiology (MIR). The general linear model will be applied to produce statistical and magnitude maps. All analyses will be done assuming a standard Boynton hemodynamic response curve; this assumption has been valid in previous experiments conducted by [name] which have examined similar brain regions of interest (ROIs) in this protocol. The statistical maps are then used to define activated regions within subjects. Random effects models for group comparisons will be performed in several ways. The increases or decreases in strength of response

(Delta S/S) will be the metric that is used. To statistically evaluate this, ROI analysis will be conducted in anatomically constrained areas along with voxel-by-voxel analysis. Both ROI-directed and voxel-by-voxel repeated measures ANOVAs (using parameters described below) are done across subjects using model estimates as inputs. Interaction effects and other activations resulting from specific comparisons of a subset of the events will be reported at an uncorrected threshold of  $p < 0.001$  for descriptive purposes. For the insular cortex, prefrontal cortex, orbitofrontal cortex, anterior cingulate cortex, and thalamic nuclei, predetermined ROIs will be used and will include any activations within these regions. A small volume correction will be applied, in keeping with the *a priori* hypotheses regarding these regions. Predetermined ROIs from the HAPN in Talairach space will be drawn using the Talairach atlas coordinate system^99 and the software ANALYZE™ will then be applied to all the participants. Regions which would not be expected to differ between the study populations will also be selected for analysis, and will provide internal activation standards to provide for the specificity of the findings (i.e., control regions). All selected ROIs will be used as a mask to constrain the regions in which test for differences are conducted. These regions will be used as a mask in an overlay on functional datasets to test the

hypotheses. Only areas with significant F-values on the ANOVA and falling within these regions will be used in statistical analyses. There will be 3 event types included in the model, resulting from the combination of all possible stimulus and response conditions: Visceral-Low distention (25-mm Hg), Visceral-High distention (50-mm Hg), and the Somatic stimulus. Voxel-by-voxel analyses will be conducted primarily to ensure that unpredicted differences a priori ROIs which are significant are not overlooked.

[figure not shown]

Figure 13: Study power as a function of sample size and effect.

**B. Sample size calculations.** The power calculations performed to assess the adequacy of the proposed sample size are based on the preliminary data, and are driven by the hypotheses proposed in Aim 2. These calculations assumed accrual of all subjects prior to the 10-week interval, a 10% attrition rate in each arm (2 subjects per group) over the course of the trial, observed group mean differences in blood flow within the anterior cingulate cortex from the IBS subjects studied in the Preliminary Studies section, and the previously reported post-desipramine reductions in ACC activations (effect size = 0.33). With the proposed sample size (n=20 per group), the anticipated 2-way ANOVA design examining the fMRI data with one between-subjects factor (Group) would be powered at 0.95 for detecting the anticipated difference using a conservative treatment effect size of 0.33, while assessment of Group x Treatment effect would be powered at 0.82 (figure 12). This sample size would allow the detection of a desipramine effect size of 0.25 at  $p<0.01$ , and also permit the interpretation of predicted non-significant interactions as consistent with the stated hypotheses. These power calculations were conducted using SamplePower v2.0 (SPSS, Inc).

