Analysis/interpretation: *Consistent with the clinical refractoriness to antidepressant therapy observed in IBS-S subjects, it is hypothesized that IBS-S subjects will exhibit a persistent pattern of abnormal HAPN activations in response to visceral stimulation following desipramine therapy.* By comparison, it is hypothesized that the IBS-No S group will exhibit decreases in HAPN activations in the post-treatment fMRI protocol (Figure 10, below). Region of interest two-way ANOVA models will be developed in comparing  $\Delta$ baseline-DES activations, with IBS Group (IBS-S and IBS-No S) as a between-subject factor. If the stated hypothesis is supported by the fMRI findings, it would suggest that the persistent HAPN activations in response to visceral afferent signals may result in the less robust clinical responses to desipramine therapy in the IBS-S. This finding would be an important addition to the existing literature, providing both insight into the central mechanisms involved in IBS antidepressant response, and also into the specific relevance of HAPN pain responses to the IBS-S subgroup.

Conversely, should HAPN activations be found to improve in both IBS groups following desipramine therapy, the possibility that HAPN visceral activations are indeed partially refractory to desipramine in IBS-S, but the detected between-group differences (IBS-S vs. IBS-No S) in post-desipramine changes in HAPN activation were smaller than expected, and thus not statistically significant. If this were the case, the ANOVA analyses would be likely demonstrate statistical trends between the IBS groups, and enrollment of additional subjects would be considered if feasible following power calculations. This additional step might lead to findings which allow for rejection of the null hypothesis.

[figure not shown]

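### HAPN specificity relies on unnamed control regions, and no planned model compares HAPN regions with control regions

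*Combined protocol and SAP*

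**What the plan says.** The ROI part of Data Analysis and Sample Size Calculations is explicit about the network: "For the insular cortex, prefrontal cortex, orbitofrontal cortex, anterior cingulate cortex, and thalamic nuclei, predetermined ROIs will be used". For the comparison regions it says only that "Regions which would not be expected to differ between the study populations will also be selected for analysis", and that they "will provide internal activation standards to provide for the specificity of the findings (i.e., control regions"). No control region is named, and no number, coordinates, time of selection or decision rule is given.

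Two sentences state what is done with the regions: "All selected ROIs will be used as a mask to constrain the regions in which test for differences are conducted", and "Only areas with significant F-values on the ANOVA and falling within these regions will be used in statistical analyses". The within-subject structure is the stimulus: "There will be 3 event types included in the model", namely two rectal distension levels and the thumb pressure. For Aim 2, "Region of interest two-way ANOVA models will be developed in comparing" the baseline-to-desipramine change between the two IBS groups. A voxel-by-voxel ANOVA is also planned, mainly to catch differences that were not predicted.

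**The concern.** A specificity statement says that an effect is larger in one set of regions than in another. The planned models can show that HAPN regions differ between groups, and separately whether a control region does. They cannot show that the two differ from each other. What remains is to set a significant result beside a non-significant one. With 20 per group, a control region carrying exactly the same effect will often miss significance. Read literally, the F-value filter adds to this: a control region without a significant F does not go forward, so it is never compared with the HAPN.

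At stake is the mechanistic reading of both Aims, which attribute pain responses and their change under desipramine to this network. In Aim 2 the exposed statement is the predicted fall in HAPN activation within IBS-No S. There is no placebo arm, so a drug or repeat-scan effect common to all regions is not removed from that within-group change. Control regions are the only device the plan names that could reveal it.

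**Working it through.** **Text check: does any model contain region?**

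| Place | Terms tested |
|---|---|
| Specific Aim 1, Analysis/interpretation | Group by somatic stimulus, within HAPN regions |
| Specific Aim 2, Analysis/interpretation | Group, on change from baseline to post-desipramine |
| Data Analysis, ROI text | Three stimulus event types; selected ROIs used as a mask |
| B. Sample size calculations | Group; Group by Treatment |

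None has a region factor or an HAPN-minus-control contrast. No rule says what follows if a control region also differs.

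**Effect size.** The plan gives no figure for specificity, so there is none to reproduce. Its effect size is 0.33 with no metric stated. Read as Cohen's f, with alpha 0.05 and two uncorrelated measures (both assumed) and 40 subjects, λ = 0.33² × 40 × 2 = 8.71. The power on F(1,38) is then 0.820, which matches the stated 0.82 for Group by Treatment. That power does not concern regions; I use it only to set d = 2 × 0.33 = 0.66. The values d = 0.8 and 1.0 are added assumptions.

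**Same true effect everywhere, two-sided t-tests at 0.05, 20 per group.** With uncorrelated regions this is closed form. The noncentrality is d × √(20/2) and the critical value on 38 df is 2.02.

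- d = 0.66: 0.66 × 3.162 = 2.09, power 0.53. One control region misses in 1 − 0.53 = 47%; all five miss in 0.47⁵ = 2.3%.
- d = 0.8: 2.53, power 0.69. One misses in 31%; all five in 0.31⁵ = 0.3%.
- d = 1.0: 3.16, power 0.87. One misses in 13%; all five in under 0.1%.

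With correlated regions I simulated 20,000 trials per setting. Percentages are among trials with a significant HAPN result, for correlations 0 / 0.5 / 0.7.

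| d | One fixed control region non-significant | At least one of five non-significant | All five non-significant |
|---|---|---|---|
| 0.66 | 47 / 32 / 24 | 96 / 70 / 54 | 2 / 4 / 4 |
| 0.8 | 31 / 21 / 16 | 84 / 54 / 41 | 0.3 / 1.8 / 1.8 |
| 1.0 | 13 / 10 / 8 | 51 / 31 / 22 | 0 / 0.3 / 0.4 |

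A direct HAPN-minus-control contrast was falsely significant in about 5% throughout.

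**Sensitivity.** With five HAPN ROIs each tested at 0.01, one control region, d = 0.66 and correlation 0.3 to 0.7, the share is 22 to 40%. If 0.33 is read as d, with 18 per group after the planned 10% attrition and one region of each type, it is 46 to 73%. In that case, however, the HAPN test itself is significant in only about 15 to 16% of trials.

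**Voxel-wise backstop.** At the descriptive p < 0.001, single-voxel power at d = 0.66 is 0.09 with 20 per group and 0.07 with 18.

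**Power of the direct contrast if the effect is truly HAPN-only** (d = 0.66, control 0, one control region, k HAPN regions averaged, correlation ρ). In units of the regional variance, the contrast has variance v = (1 + (k − 1)ρ)/k + 1 − 2ρ. Its noncentrality is 0.66/√v × √(20/2).

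- k = 1, ρ = 0.3: v = 1.40, noncentrality 1.76, power 0.41.
- k = 5, ρ = 0.7: v = 0.36, noncentrality 3.48, power 0.92.

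At 18 per group the corresponding range is 0.37 to 0.89.

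**The case against.** **Specificity is not a stated hypothesis or endpoint.** Both hypotheses and both primary endpoints ask whether HAPN activation differs between groups, not whether it differs more than elsewhere. This stands: those tests are valid without a region factor, and only an interpretation built on them is affected.

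**Choice after the data.** A reader might infer that a convenient control region can always be picked once results are known. The documents do not support that. The rule given is prior expectation of no difference, and nothing provides for choosing by outcome. The at-least-one-of-five column needs selective reporting that the plan neither states nor excludes. Even then it runs from 22 to 96%, not to certainty.

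**Several control regions protect well.** The plan speaks of regions in the plural. If all must be non-significant, the risk is about 0 to 4% with five regions, so it does not follow that a brain-wide effect would be reported as HAPN-specific. The plan sets neither the number nor the rule, so this protection is possible but not secured.

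**A vascular effect of desipramine.** A reader might infer that it biases the main Aim 2 comparison. Both groups receive the drug, so an effect common to both cancels in the between-group comparison of change. It does not cancel in the within-group IBS-No S decrease. The Aim 2 limitations already concede that HAPN change could arise outside the HAPN.

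**Other safeguards.** The voxel-by-voxel analysis is real but weak at this sample size, and no specificity rule is attached to it. Scaling whole-brain intensity across runs and using a relative signal metric bear on global signal differences, but they test nothing regional.

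**The contrast is not a complete answer.** Its 5% error holds for an equal additive shift. Suppose instead that an effect scales all responses: an assumed 40% gain giving HAPN d = 0.8, control response 20 to 50% of the HAPN response, and correlation 0.3 to 0.7. The contrast is then significant in 17 to 72% of trials without any specificity. This stands as a limit of the remedy.

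**Conclusion.** The point holds as a gap in the specificity interpretation. The control regions are unnamed and no model tests HAPN against them, so the plan's own specificity device would work by comparing significance levels. With one fixed control region and a uniform true effect, it would suggest specificity wrongly in about 8 to 47% of trials with a significant HAPN result. With five control regions all required to be non-significant, the figure is about 0 to 4%. These ranges rest on assumed effect sizes (d = 0.66 to 1.0), 20 per group and equal between-region correlations of 0 to 0.7. The documents give only 0.33 without a metric and no correlation.

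The finding does not undermine the primary HAPN group tests in either Aim. It bears on any statement that an effect is particular to the HAPN, and most directly on the IBS-No S decrease in Aim 2. The change should be made, but the design does not depend on it.

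**What to change.** Before analysis, and without new data:

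1. Name the control regions, with Talairach coordinates and their number, on anatomical grounds. Do not choose them because they were non-significant in the pilot. With 8 per group, pilot power at d = 0.8 is 0.32, so about 68% of regions with that true difference would pass. The pilot also used rectal distension only, and its Table 2 reports HAPN regions only.
2. Aim 1: add a Group by Region-type contrast, computed per subject as mean HAPN Delta S/S minus mean control-region Delta S/S.
3. Aim 2: test the group difference in change of that quantity, and report its within-group change in IBS-No S.
4. Exempt the control regions from the F-value filter, so that they are always reported.
5. State that HAPN specificity is claimed only from these contrasts, and say what is concluded if a control region also differs.
6. Report each region type's overall response beside the contrast, because a proportional effect can produce a Group by Region-type difference.

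The cost is some analysis wording and a few contrasts on data already planned. The specificity claim also becomes harder to make. Power is about 0.4 to 0.9 at d = 0.66, depending on between-region correlation and how many HAPN regions are averaged, and this should be stated. A non-significant contrast would leave specificity undecided; it would not refute it.

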## ***Regional activations within the HAPN by study group***

[figure not shown]
Consistent with findings previously reported in the literature, during noxious visceral stimulation a significant difference in a HAPN brain region activations was seen in comparing IBS subjects and healthy controls (Table 2 and Figure 7). Between-comparison of HAPN activations in the IBS-S and IBS-No S groups revealed significantly greater activation of the right prefrontal cortex, insula, and thalamus in the IBS-S subjects. The

IBS-S subjects also were found to have greater activation of the bilateral anterior cingulate and orbitofrontal cortices compared to their IBS-No S counterparts.

[figure not shown]
**Table 2: Regional differences in cerebral activations within the homeostatic afferent processing network (HAPN) in response to visceral stimulation in IBS-S subjects compared to controls, and IBS-S compared to IBS-No S subjects.**

Region	Hemisphere	Coordinates (x,y,z)*	All IBS vs. Controls		IBS-S vs. IBS-No S	
			Z	p	Z	p
Anterior cingulate cortex	Left	-8, 38, 16	2.91	0.004	2.67	7.3 x10 
	Right	9, 34, 11	2.19	0.02	4.15	7.6 x10 
Insula	Left	-39, 2, 7	5.20	9.7 x10 	1.09	0.27
	Right	32, 23, 10	5.47	2.8 x10 	2.33	0.02
Orbitofrontal cortex	Left	-25, 13,-10	4.27	1.9 x10 	3.13	0.001
	Right	34,22,-3	4.82	1.4 x10 	4.84	6.5 x10 
Prefrontal cortex	Left	-41, 40, 11	4.87	5.4 x10 	1.37	0.16
	Right	41, 50, 5	5.78	3.5 x10 	4.17	2.4 x10 
Thalamus	Left	-19, -22, 11	5.58	1.2 x10 	1.51	0.12
	Right	12, -8, 11	4.02	5.8 x10 	2.09	0.003

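### The sample-size paragraph lets predicted null interactions count as consistent with the hypotheses without a margin, and several of its power inputs conflict with other sections

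*Combined protocol and SAP*

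**What the plan says.** All of this is in the combined protocol and SAP, under Data Analysis and Sample Size Calculations, part B, unless another section is named.

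- **Powers.** The two-way ANOVA "would be powered at 0.95 for detecting the anticipated difference using a conservative treatment effect size of 0.33". For the interaction, the text says that "assessment of Group x Treatment effect would be powered at 0.82 (figure 12"). The group size given is 20.
- **Inputs.** The calculation "assumed accrual of all subjects prior to the 10-week interval, a 10% attrition rate in each arm (2 subjects per group"). One effect input is the "observed group mean differences in blood flow within the anterior cingulate cortex from the IBS subjects studied in the Preliminary Studies section". For the drug effect the paragraph turns to reference 33 and takes from it the "previously reported post-desipramine reductions in ACC activations (effect size = 0.33").
- **A second claim.** "This sample size would allow the detection of a desipramine effect size of 0.25" at p<0.01; no power is attached.
- **Null results.** The sample size is said to "permit the interpretation of predicted non-significant interactions as consistent with the stated hypotheses".

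Elsewhere, Hypothesis 2 predicts persistent activation in IBS-S and improvement in IBS-No S after desipramine. The Aim 2 Design and Methods text and Figure 9 make the post-treatment difference between groups the primary endpoint. The Aim 2 Analysis/interpretation text compares change from baseline between groups.

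**The concern.** Failing to find an interaction in a small sample is weak evidence that none exists. A rule that lets a non-significant result count in favour of a hypothesis, with no margin and no statement of which tests it covers, supports a conclusion that the data may not carry.

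This paragraph is also the plan's only sample-size justification. The effect-size metric, the alpha for 0.95 and 0.82, and the correlation between the two scans are not given in the visible text. Nor is it clear whether the powers refer to 20 or 18 per group. Several inputs that are given disagree with other sections. A reader therefore cannot tell what between-group difference in change the study can detect, and so cannot judge what a null interaction would mean.

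**Working it through.** **1. Where the plan gives power 0.82.** The inputs are 20 per group (N = 40) and effect size 0.33. Assumed, because not stated: Cohen's f, two-sided alpha 0.05, two groups by two scans, pre/post correlation rho. For Treatment and for Group x Treatment the noncentrality is 2·N·f²/(1 − rho), with 1 and N − 2 df.
- N = 40, rho = 0: 2 × 40 × 0.33² = 8.71, power 0.82. This matches the plan.
- N = 36 (the plan's own 18 completers per group), rho = 0: 7.84, power 0.78.

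**2. Where the plan gives power 0.95.** There are two possible routes.
- *Treatment effect, f = 0.33.* Power is 0.95 at rho of about 0.36 (N = 40) or 0.43 (N = 36). Treatment and interaction share df and error term, so at that rho the interaction's 0.82 would correspond to an f of about 0.26, which the text does not state.
- *Preliminary group difference.* Table 2, headed "Regional differences in cerebral activations within the homeostatic afferent processing network (HAPN"), gives an anterior cingulate Z of 2.67 (left) for IBS-S against IBS-No S, with 8 per group. Read as a two-sample statistic, d is about 2.67 × √(2/8) = 1.34. A single-scan group comparison needs d = 1.17 (20 per group) or 1.24 (18) for power 0.95. At d = 1.34 power is 0.98 or 0.97.

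So each figure is reachable, but the text does not say by which route.

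**3. What a null interaction can show.** With 18 completers per group, the 95% half-width for the difference in mean change is t(0.975, 34) × √(2/18) = 2.03 × 0.333 = 0.68 SD of change. Multiplying by √(2(1 − rho)) gives 0.96, 0.80, 0.68 or 0.52 SD of activation at rho 0, 0.3, 0.5 or 0.7. For an equivalence claim (two one-sided tests at 0.05, true difference zero), a margin of 1.0 SD of change gives power of about 0.81 by simulation.

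**4. What the change contrast can detect.** With 18 per group and two-sided alpha 0.05, power 0.82 needs a difference of 0.99 SD of change. That is 1.40, 1.17, 0.99 or 0.76 SD of activation at rho 0, 0.3, 0.5 or 0.7. This is for one region, before any multiplicity correction.

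**5. The claim of 0.25 at p<0.01.** Read as f for a within-subject effect with 18 per group, power is 0.29, 0.61 or 0.87 at rho 0, 0.5 or 0.7. The claim means little until its power and correlation are stated.

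**6. Conflicts between sections.**

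| Sample-size paragraph | Elsewhere |
|---|---|
| 0.33 labelled as a desipramine effect, reference 33 | Background section 4 and the reference list: reference 33 is an amitriptyline study |
| 10-week interval | Aim 2 Design and Methods, Figure 9: 4-week course, second scan at week 4 |
| Power shown in figure 12 | Figure 12 is the distention protocol; the power caption is Figure 13 |
| Contrast behind 0.95 not named | Aim 2 endpoint is the post-treatment group difference; the Aim 2 analysis is of change |

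**The case against.** The strongest reply is that nothing is shown to be miscalculated. A reader might infer an error from the fact that a single 0.33 at one non-negative correlation cannot give both 0.95 and 0.82 in a two-scan design. The plan does not claim that it does: it also names the preliminary anterior cingulate difference, and steps 1 and 2 give a workable route to each figure. Figure 13 is not shown and, by its caption, plots power against sample size and effect, so it may hold some of the missing inputs. The 0.33 may also be meant to carry over to the interaction. All of this stands.

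A second reply is that the clause covers only predicted nulls. A reader might infer that a null result on Hypothesis 2 itself would be claimed as support. The documents do not say so. Hypothesis 2 predicts a difference, and the Aim 2 Analysis/interpretation text treats a non-significant group difference in change as possibly a matter of low power. The clause may refer to the control regions described in the data analysis section. This also stands, but the clause does not name them, and a predicted null still needs a margin before non-significance can count for it.

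Third, the standardised differences in steps 3 and 4 rest on assumed alpha and correlations and on a single region. That is fair, and they are shown as ranges for that reason.

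**Conclusion.** The null-interaction clause should not stay as written. With 18 completers per group, the interval around a null difference in change still spans about 0.68 SD of change either way, and an equivalence reading with about 0.80 power would need a margin near 1.0 SD. Both figures are in SD of change, so they need no correlation assumption; they do assume the plan's 10% attrition and a two-group comparison of change in one region.

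The drug label, the interval and the figure pointer conflict with other sections on the face of the text, as do the two descriptions of the Aim 2 contrast. For 0.95 and 0.82 the conclusion is limited: they cannot be verified from the visible text, which is not the same as being wrong. On the route that reproduces 0.82, moving from 20 to 18 per group lowers it to 0.78.

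**What to change.** 1. **Null interactions.** Replace the clause with: *A non-significant interaction will be reported with its 95% CI and will not by itself be taken as consistent with the hypotheses.* If nulls in control regions are meant, say so and give a margin.
2. **Power statement.** Say whether 0.95 and 0.82 are for 20 or 18 per group, which effect each uses (the preliminary anterior cingulate difference or 0.33), and the metric, alpha and correlation. If the preliminary difference is used, give its mean and SD. Add: *With 18 completers per group, two-sided alpha 0.05 and a single region (anterior cingulate) before any multiplicity correction, a between-group difference of about 0.99 SD of change is detected with power 0.82.* Give the power for 0.25 at p<0.01, or withdraw that claim.
3. **Consistency.** Attribute 0.33 to the amitriptyline study that it cites. Reconcile the 10-week interval with the week-4 scan. Correct the figure pointer. Reconcile the post-treatment endpoint with the change analysis, so that the power statement names the contrast it covers.

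The cost is text and a recalculation, with no added patients, visits or scans. The stated power may become slightly less favourable.
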